10. ENDPOINTS

- *Describe the primary and secondary study endpoints*
- *Describe any primary or secondary safety endpoints*

This study is a feasibility pilot whose primary objective is to assess the acceptability, scalability of implementation, and participant satisfaction with a personalized trial methodology to resolve a chronic complaint. Thus, the primary endpoint is the system usability scale (SUS) $\geq 85^{22}$.

11. RESEARCH PROCEDURES

- *Include a detailed description of all procedures to be performed on the research subject and the schedule for each procedure.*
- *Include any screening procedures for eligibility and/or baseline diagnostic tests*
- *Include procedures being performed to monitor subjects for safety or minimize risks*
- *Include information about drug washout periods*
- *If drugs or biologics are being administered provide information on dosing and route of administration*
- *Clearly indicate which procedures are only being conducted for research purposes.*
- *If any specimens will be used for this research, explain whether they are being collected specifically for research purposes.*
- *Describe any source records that will be used to collect data about subjects*
- *Indicate the data to be collected, including long term follow-up*

Potential participants who self-identify as having sleep quality concerns via in-person or virtual recruitment methods will be directed to an information site with details about the pilot study. Those who are interested in participating in this pilot study will be directed to undergo a cell-phone confirmation via text and to sign a HIPAA Authorization form before completing an initial screening survey process. The HIPAA Authorization will be electronically signed via the N1Thrive by 4Peacocks platform. The initial screening process includes identifying symptoms on the validated Insomnia Symptom Questionnaire (ISQ), as well as questions pertaining to inclusion and exclusion criteria. Consenting coordinators will review these data and determine whether or not a potential participant is eligible to

participate. Those who are eligible will receive a link to a short video about key details from the consent form, as well as an electronic copy of the consent form. Potential participants will also be given the option to set up a 30-minute phone call with a research coordinator, where the research coordinator will describe the study process and offer an additional opportunity for the potential participant to ask any questions. After completing or opting out of the phone call, the potential participant will be sent a link to view and electronically sign the consent form via the N1Thrive by 4Peacocks platform. Before being able to sign and submit the consent form, potential participants must demonstrate understanding of the protocol by correctly answering 4 questions pertaining to the information presented in the consent form.

Once potential participants successfully submit their signed consent form, they will receive an onboarding questionnaire to collect more information, including a home address. A Consenting Coordinator will review this information and send the potential participant a text which will include a confirmation of the start date of their baseline period, as well as a link to a short video of what to expect during onboarding to the study. They will be receive an initial study kit including a Fitbit device via mail, and will receive a copy of their electronically signed HIPAA authorization and consent form with a URL to view the informed consent video that they watched previously.

All baseline periods will begin on a Monday. No more than 20 participants will be permitted to begin on the same day. The baseline period will take place over the course of 2 weeks. Potential participants will not receive any melatonin or placebo pills during the baseline period, and they will be asked to refrain from taking any melatonin on their own. Participants will be instructed to continue treating their sleep quality issues as they normally would.

At three randomized times each day during waking hours (identified by the potential participant during their onboarding survey), baseline participants will receive a text message asking them to rate their pain, fatigue, concentration, confidence, mood, and stress levels at that exact moment. Each morning, baseline participants will receive a survey asking a few questions about their sleep quality the previous night using a modified version of the Consensus Sleep Diary, as well as factors that may have contributed to any sleep issues. At the end of the baseline period on Sunday evening, baseline participants will receive a slightly longer survey that includes the Insomnia Severity Index.

During the baseline period, potential participants will be asked to wear their Fitbit all day and night, even while they are sleeping. Participants will be asked to download the Fitbit app to their smart phone. Baseline participants will be instructed to sync their Fitbit device by opening the Fitbit app on their phone at least every two days and to charge their device at least every four days.

Ten days into the baseline period, a Consenting Coordinator will review individual adherence to Fitbit wear and to survey responses. Adherence to Fitbit wear will be defined as recorded activity of greater than 12 hours a day, and recorded sleeping activity greater than 180 minutes in total. Survey adherence will be defined as submission of a given survey. Baseline participants who do not achieve at least 80% adherence of Fitbit wear and survey submission during the first 10 days of the baseline period will be given until day 14 of the trial to obtain 80% adherence. Those who still do not meet 80% adherence by day 14 will be withdrawn from the study. Those participants who do maintain at least 80% adherence during the baseline period will be randomized to one of two intervention sequences in the pilot study. Participants who are randomized to receive intervention sequences will receive confirmation including their protocol timeline. Participants will also receive a second mailed kit including medication adherence devices containing pills of a 3mg dose melatonin, pills of a 0.5mg dose melatonin, and pills of a placebo. Participants will not know when they are taking 3 mg melatonin, 0.5 mg melatonin or placebo (single blinded). Enrollment will continue until up to 60 participants have been randomized overall, with 30 participants randomized to receive ABCCBA and 30 participants randomized to receive CBAABC.

Each intervention sequence is made up of 6 2-week periods assigning either 3mg dose melatonin, 0.5mg dose melatonin, or placebo. Participants will not be aware of which pill they are taking in assigned intervention weeks. Instead, they will receive a text notification each night asking them to take one pill out of a designated container (A, B, or C) 1 hour before bed. Melatonin or placebo will be tracked remotely through electronic adherence pill bottles that record each event of a pill being removed via a cellular connection to a de-identified dashboard. Throughout each intervention sequence, participants will be asked to refrain from taking additional melatonin on their own.

Melatonin and placebo supplements will be stored at the study team office from delivery until time of dispensation to participants upon their randomization into the intervention period. The supplements will be handled only by study personnel and stored according to labeling. Records of the batch numbers of supplements provided to each participant will be maintained.

During all intervention weeks (12 weeks total), participants will be asked to continue wearing their Fitbit device each day and night. They will continue to receive 3 randomized text message surveys each day with questions about their pain, fatigue, concentration, confidence, mood, and stress at that current moment, as well as a morning text asking them to report on their sleep quality the previous night, using a modified Consensus Sleep Diary. Morning surveys during the intervention weeks will also include questions about any melatonin or placebo-related side-effects the participant is experiencing. At the end of each intervention period on Sunday evening (every two weeks), participants will receive a slightly longer survey that includes the Insomnia Severity Index. A study phone number and email address will be available as part of each survey to contact the study team

if a participant is concerned about any side effects they are experiencing. Participants will be instructed to contact 911 or go to the nearest emergency room in the event of a medical emergency. In addition, participants will be advised to stop taking their pills if they are concerned about side effects.

Participants may receive additional text messages to those outlined above with important reminders about their protocol (e.g., transition to a new intervention period), or to remind participants to sync their data or charge their devices. We will send a maximum of 5 text message surveys per day during the study, as well as text messages of these reminders and other important study communications.

In the event of an unanticipated circumstance that temporarily prevents a participant from completing study activities (illness, injury, death in the family, etc.), the participant will have the option of pausing their study to resume once their circumstance has been positively resolved.

Participants will complete remote data monitoring after they have gone through one baseline period (two weeks), two 3mg dose melatonin intervention periods (two weeks each), two 0.5mg dose melatonin intervention periods (two weeks each), and two placebo periods (two weeks each), or 14 weeks total. Alternatively, a participant may choose to withdraw from the study, or be withdrawn from the study by the research team. Upon completion of data monitoring, participants will be given instructions on how to un-link their Fitbit from the study account. Melatonin or placebo adherence tracking will be suspended, as will daily text messages and survey prompts.

We will compile the self-reported data from questionnaires, side effects, pain, fatigue, concentration, confidence, mood, and stress assessments, as well as information from the Fitbit regarding activity (steps, heart rate, flights climbed and intensity) and sleep (duration, estimated sleep stages) for each individual participant. Melatonin or placebo adherence will be tracked via a study dashboard connected to the pill bottle adherence device and will be included in the compiled data. No identifying information associated with participants will be provided to Nomi, the medication adherence device company, or included on the adherence report provided by Nomi. We will analyze this data and create a summary report of the participant's observed data over the study period, in relation to the 3mg melatonin, 0.5mg melatonin, and placebo intervention periods.

The participant will be sent this report in a secure text through the N1Thrive platform by our study team. Participants will also be sent links to several online videos explaining the terms and data visualizations available in their summary report. These videos will be general to the template report and will not contain any individual results or health information. Participants will be sent a satisfaction survey after receiving their individual report. Study participation will end upon completion of the satisfaction survey.

The satisfaction survey will be sent via text up to three times before a research coordinator will attempt to call individual participants to complete the satisfaction survey via phone.

After completion of the satisfaction survey, participants will be asked to participate in a virtual interview with a member of our study team to discuss their study experience. We will ask several questions about their experience and opinion toward Personalized Trials, as well as ask for suggestions for improvement. All interviews will be audio-recorded and transcribed via Microsoft Teams (or equivalent program) to ensure full capture of information provided during the discussion. Participants will be informed that the session will be recorded prior to initiating the interview. If the participant declines to be recorded, they may still participate in the interview and the study team will take notes of the conversation. Audio and transcription files will be stored securely on the PHI-approved SharePoint server.

Participants will be provided with instructions regarding how to return the used Nomi bottles, Nomi charger, and any unused pills to the research team to be properly disposed of. The research team will return the Nomi bottles to the manufacturer for proper sanitization and disposal. Used Nomi chargers will be stored at the research office. Unused pills will be disposed of in line with FDA and Environmental Protection Agency guidelines for disposals of over the counter supplements.

Participants will be mailed a pay card (ClinCard) valued at \$100 after successful completion of the satisfaction survey as well as the successful return of the used Nomi medication adherence devices to the research team.

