The randomization schedule will be set up by a member of the Institute of Health System Science data team and provided to the data analyst assigned to Personalized Trials to Improve Sleep Quality. Randomization will occur with a fixed seed value for the purposes of repeatability and auditability, and the list of 60 participants will be split into two groups of 30 using a random shuffle function that takes that seed as input. The order in which an individual becomes eligible for one of these 60 randomizations will determine the placement given (i.e. the first person eligible will be randomized to the intervention order given to participant 1, and continue sequentially). Eligibility is obtained by a participant maintaining at least 80% adherence of survey response, Fitbit wear ≥ 12 hours a day 80% of days, and 80% sleep data ≥ 180 minutes available through the baseline run-in period. The data analyst will alert the research coordinator of the assigned randomization once a participant becomes eligible during the baseline run-in period. As this pilot is not blinded to study coordinators, this concealed allocation involving the data analyst alerting the study coordinator of intervention assignment will be used to prevent bias by blinding the sequence up until time of randomization.

The primary outcome measure will be a mean usability score, obtained using the System Usability Scale (SUS), a validated 10-item questionnaire originally developed by John Brooke in 1986 that asks users to score each item on a Likert scale from Strongly Disagree (rating of 1) to Strongly Agree (rating of 5). The SUS will be presented to the participant as addressing the ease of use, complexity, consistency of the Personalized Trials system as a whole, from recruitment to receipt of the report. Individual results are calculated to arrive at a composite measure out of 100. Participant SUS scores will be averaged together. Higher scored values correlate to a more usable system, and therefore a better outcome.

Other secondary outcome measures which assess the feasibility of the Personalized Trials framework include:

- Mean participant satisfaction with Personalized Trials components supplemental to the SUS,
- Qualitative satisfaction data collected during the virtual participant follow-up interview,
- Mean participant survey adherence rate, defined as completion of each assigned survey

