- Mean participant Fitbit adherence rate, defined as recorded heart rate data for \geq 12 hours each day,
- Mean participant Fitbit sleep rate, defined as recorded sleep and wake cycles
- Mean participant melatonin adherence rate, defined as retraction of the appropriate pill from adherence device on assigned nights
- Mean participant placebo adherence rate, defined as retraction of the appropriate pill from adherence device on assigned nights

In order to share a summary report of observed trends back to the participant to assess acceptability and satisfaction with the participant report, additional secondary outcomes will be analyzed on an N-of-1 level including:

- Mean Within-Subject Difference in self-reported symptoms of sleep disturbance using the Insomnia Severity Index (ISI) during 3 treatment periods from Mean Baseline
- Mean Within-Subject Difference in self-reported sleep quality using a modified version of the Consensus Sleep Diary during 3 Treatment Periods from Mean Baseline
- Mean Within-Subject Difference in Ecological Momentary Assessment Three-Times-Daily of Pain During 3 Treatment Periods from Mean Baseline, using the Numeric Pain Rating Scale adapted from McCaffery, Beebe et al. 1989
- Mean Within-Subject Difference in Ecological Momentary Assessment Three-Times-Daily of Fatigue During 3 Treatment Periods from Mean Baseline, using the Numeric Pain Rating Scale adapted from McCaffery, Beebe et al. 1989
- Mean Within-Subject Difference in Ecological Momentary Assessment Three-Times-Daily of Concentration During 3 Treatment Periods from Mean Baseline, using the Numeric Pain Rating Scale adapted from McCaffery, Beebe et al. 1989
- Mean Within-Subject Difference in Ecological Momentary Assessment Three-Times-Daily of Confidence During 3 Treatment Periods from Mean Baseline, using the Numeric Pain Rating Scale adapted from McCaffery, Beebe et al. 1989
- Mean Within-Subject Difference in Ecological Momentary Assessment Three-Times-Daily of Mood During 3 Treatment Periods from Mean

Baseline, using the Numeric Pain Rating Scale adapted from McCaffery, Beebe et al. 1989

- Mean Within-Subject Difference in Ecological Momentary Assessment Three-Times-Daily of Stress During 3 Treatment Periods from Mean Baseline, using the Numeric Pain Rating Scale adapted from McCaffery, Beebe et al. 1989

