16. WITHDRAWAL OF SUBJECTS

- *Describe anticipated circumstances under which subjects will be withdrawn from the research without their consent*
- *Describe procedures for orderly termination*
- *Describe procedures that will be followed when subjects withdraw from the research, including partial withdrawal from procedures with continued data collection.*

Circumstances under which participants may be withdrawn from the research without their consent include failure to maintain protocol adherence, ,self-reported

adverse side effects to two or more interventions, significant cell phone carrier issues that prevent the participant from receiving study text messages, it is not in the participant's best interest to continue in the pilot, and the pilot study is stopped. We will not withdraw a participant based on non-adherence to wearing their Fitbit, taking their supplement, or completing daily surveys, as this absence of data is useful for feasibility purposes. Because of this, lack of adherence to Fitbit wear, taking the supplements, or completion of daily surveys are not considered protocol deviations.

A potential participant will not be randomized to receive the intervention protocol until he/she has demonstrated at least 80% adherence to continuous Fitbit monitoring (activity recorded > 12 hours/day, and recorded sleep activity) and response to survey questionnaires during the baseline period.

Potential participants will be notified of the possibility of being removed from the study before intervention randomization due to adherence issues in the informed consent. Participants who fail to maintain minimum adherence during baseline will be notified by the research team in the first 10-14 days of baseline participation. These participants will stop receiving notifications and survey prompts and will receive instructions to un-link their Fitbit device. The participant will be able to keep their Fitbit.

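### The 80% baseline survey gate does not secure the single baseline ISI, so a participant can be randomised whose planned ISI change from baseline cannot be computed

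*Combined protocol and SAP*

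**What the plan says.** Section 11 (Research Procedures) sets a 14-day run-in starting on a Monday: "The baseline period will take place over the course of 2 weeks". Each day brings three momentary surveys at random waking times and one morning sleep diary. The ISI comes once: "At the end of the baseline period on Sunday evening, baseline participants will receive a slightly longer survey that includes the Insomnia Severity Index". That is day 14.

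The gate appears in three places:

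- Section 11 defines the unit, "Survey adherence will be defined as submission of a given survey", schedules a review at day 10, and adds: "Those who still do not meet 80% adherence by day 14 will be withdrawn from the study".
- Section 12 (Statistical Analysis): "Eligibility is obtained by a participant maintaining at least 80% adherence of survey response". The two Fitbit criteria, wear and sleep data, each have their own 80% threshold there. Section 12 also has the data analyst release the assignment when the participant becomes eligible during the run-in.
- Section 16 (Withdrawal of Subjects) asks for 80% adherence to Fitbit monitoring and "response to survey questionnaires during the baseline period".

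Among the secondary outcomes in Section 12 are the within-subject difference in "self-reported symptoms of sleep disturbance using the Insomnia Severity Index (ISI) during 3 treatment periods from Mean Baseline", a matching difference for the sleep diary, and the feasibility measure "Mean participant survey adherence rate, defined as completion of each assigned survey".

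**The concern.** The ISI baseline is a single observation. It is requested after the day-10 review, on the last day of the gate and, under the Section 12 wording, possibly after allocation has been released. Screening uses the Insomnia Symptom Questionnaire, a different instrument, so there is no second baseline ISI to fall back on. None of the three statements of the gate requires the ISI or sets a minimum number of diaries, although both instruments feed outcomes defined against baseline. No rule covers a missing baseline.

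Two things are at stake. One is a listed secondary outcome that is lost for any participant who misses one text. The other is the feasibility conclusion on data collection: an adherence rate dominated by momentary texts can look high while the instruments that measure the sleep complaint are poorly completed.

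**Working it through.** **Inputs (Section 11).** Three momentary surveys and one diary per day; one ISI survey at the end of baseline and at the end of each of the six two-week periods; 14 baseline days and 84 intervention days; threshold 80%.

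**Check against the plan's own figure.** The busiest day has 3 + 1 + 1 = 5 surveys. This agrees with the cap of five text surveys a day in Section 11, so the schedule has been read correctly.

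**Baseline gate, all surveys pooled.**

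- Surveys issued: 14 × 3 + 14 × 1 + 1 = 42 + 14 + 1 = 57.
- Needed: 0.80 × 57 = 45.6, so 46; 11 may be missed.
- Missing only the ISI: 56/57 = 98.2%, a pass.
- If the ISI is not counted: 56 surveys, 0.80 × 56 = 44.8, so 45 needed, and the ISI is not tested at all.

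Neither count can enforce the ISI.

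**How often might it be missing?** The documents give no rate. For a participant exactly at the threshold, with 11 of 57 missed at random, the chance that the ISI is among them is 11/57 = 19%. Better adherers would have a lower chance. Assuming 5% to 20% of 60 participants miss it gives 3 to 12 people without an ISI change score.

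**Diaries.**

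- Fewest that can pass: 46 − 42 = 4 of 14 with no ISI, or 46 − 42 − 1 = 3 with the ISI. If the ISI is not counted, 45 − 42 = 3.
- Precision, assuming independent nights of equal variance: the SE of the baseline mean relative to 14 nights is √(14/4) = 1.87 or √(14/3) = 2.16.
- For the change from baseline with 28 treatment nights, the ratio is √(1/k + 1/28) / √(1/14 + 1/28), which is 1.63 for k = 4 and 1.86 for k = 3.
- A milder passing case misses 7 diaries, the ISI and 3 momentary surveys (57 − 11 = 46). The ratio is then √(1/7 + 1/28) / √(1/14 + 1/28) = 1.29.
- With 11 misses at random, the expected number of diaries is 14 × 46/57 = 11.3, and the chance of 4 or fewer is about 2 in 10 million.

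**Survey-adherence outcome, pooled.**

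- Momentary share at baseline: 42/57 = 73.7%.
- Intervention: 84 × 4 + 6 = 342 surveys, of which 84 × 3 = 252 are momentary (73.7%).
- All six ISIs missed, everything else done: 336/342 = 98.2%.

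**The case against.** Several points on the other side stand.

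- Pooling is not stated. The definition in Section 11 says when one survey counts as adherent; it does not say that every type enters one denominator. Pooling is the natural reading, helped by the fact that Section 12 splits the Fitbit criteria but not the surveys, but it remains a reading.
- A reader might infer that both sleep outcomes lose their baseline. The documents support this only for the ISI. Three or four diaries still give a mean, and the plan sets no minimum below which it is unusable. That case also needs all 42 momentary surveys answered while 10 or 11 diaries are skipped.
- A reader might infer that a missed baseline makes the six later ISI scores worthless. It does not. Section 11 describes the personal report as relating observed data to the three intervention conditions. Contrasts between conditions do not need the baseline, because it cancels.
- The day-10 review is interim. Sections 11 and 12 look to adherence over the whole baseline, so passing at day 10 is not a final pass.
- Section 11 gives no closing time for the Sunday survey, so a late answer may be possible. Nor, however, does it describe any follow-up of a missing ISI, whereas the satisfaction survey is sent up to three times and then pursued by phone.
- The ISI and diary changes are secondary, individual-level outcomes. The primary endpoint is the System Usability Scale.

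These points narrow the concern without removing it: the listed ISI outcome still depends on one survey that the gate does not require.

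**Conclusion.** The point holds in a limited form. On the pooled reading, a participant who misses only the baseline ISI passes at 98% and is randomised, and that person's ISI change from baseline cannot be computed. How many would be affected is unknown; 3 to 12 of 60 follows from an assumed 5% to 20% miss rate. The upper end is close to the 19% that applies only to someone at the gate minimum with random misses.

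The diary baseline can be thin but not absent, and the extreme case is very unlikely unless participants avoid diaries systematically. The pooled adherence rate is about three-quarters momentary texts and can conceal poor completion of the sleep instruments. Between-condition comparisons and the primary endpoint are untouched. This is an inexpensive improvement to a secondary outcome and to the feasibility reporting, not a flaw in the main result.

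**What to change.** - **Section 11 (baseline period and adherence review):** open the baseline ISI a day or two before day 14, with reminder texts on the existing platform.
- **Sections 11 and 12 (randomisation):** require the baseline ISI to be submitted before the analyst releases the allocation.
- **Section 12 (secondary outcomes):** report survey adherence separately for momentary surveys, morning diaries and ISI.
- If the sponsor intends the 80% rule as something other than a pooled count, the three statements of the gate should say so.

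The cost is protocol wording and a reminder rule, plus a few participants delayed or lost before randomisation because they do not submit the ISI. I would not go further and apply the 80% threshold to each survey type. That would select more compliant users into a pilot whose purpose is to measure adherence and usability, and separate reporting already shows where completion is weak.

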9. STUDY TIMELINES

- *Describe the duration of an individuals participation in the study*
- *Describe the duration anticipated to enroll all study subjects*
- *The estimated date of study completion*

The study will take place over the course of 14 weeks. The first two weeks will be a baseline period, where no supplement is assigned, but data are collected, including self-report of sleep quality and duration and accelerometer-derived sleep and activity data. After successful completion of the baseline period, participants will be randomized to six 2-week intervention blocks of a 3mg dose melatonin, a 0.5mg dose melatonin, and a placebo. At the end of the 14 weeks, a report containing the individual's observed data will be prepared for each participant and electronically sent to them along with a satisfaction survey (electronic, or phone if they are non-responders). Creating this type of participant report will help to assess the feasibility of using a N-of-1 trial design through user-acceptability of sleep quality and wellness-related data visualizations and the ability to choose preferred intervention (if any) based on the data. This report will be sent within 3 months of study completion. A \$100 pay card (ClinCard) will be sent to each participant as compensation for their time after the successful completion of 14 weeks of data collection, satisfaction survey, and return of the Nomi smart bottles to the manufacturer. After the satisfaction survey is completed, study coordinators will reach out to each participant with an invitation to virtually interview them about their experience in Personalized Trials.

Potential participants will have the opportunity to provide preferences of start dates during their enrollment process. The study team will confirm applicability of the

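### Does the day-14 catch-up fail for Fitbit wear, and does it leave too little time to mail the pills?

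*Combined protocol and SAP*

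**What the plan says.** Section 11 (Research Procedures) defines Fitbit adherence by hours of recorded activity per day and minutes of recorded sleep, and survey adherence by submission. Adherence is reviewed ten days in. Participants below 80% "during the first 10 days of the baseline period will be given until day 14 of the trial to obtain 80% adherence"; those still below are withdrawn. Section 12 (Statistical Analysis) lists survey response, wear and sleep data as separate 80% criteria, scores wear as a share of days, and applies them over the baseline run-in. Participants are asked to "sync their Fitbit device by opening the Fitbit app on their phone at least every two days".

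On the calendar, Section 11 says "All baseline periods will begin on a Monday", and the longer survey is sent "At the end of the baseline period on Sunday evening". Intervention periods also close on Sundays, and the total is 14 weeks.

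On supplies, the pills stay at the study office "until time of dispensation to participants upon their randomization into the intervention period". "Participants will also receive a second mailed kit including medication adherence devices". Section 11 also says "Potential participants will not receive any melatonin or placebo pills during the baseline period".

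On allocation, Section 9 (Study Timelines) says "After successful completion of the baseline period, participants will be randomized to six 2-week intervention blocks", whereas Section 12 has the analyst pass on the assignment when a participant becomes eligible within the run-in.

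**The concern.** The catch-up names Fitbit wear as well as surveys, yet simple counting suggests that it cannot succeed for wear. A participant could wear the device perfectly for four more days and still be withdrawn, or coordinators might improvise an entry rule.

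The calendar has no slack for mailing. If kits arrive late, the lost nights fall only on the condition in first position: 3 mg in one sequence, placebo in the other, never 0.5 mg. Section 12 counts pill adherence over assigned nights and does not say whether nights before delivery count. Postal delay could then look like participant non-adherence, and nights without pills could enter that condition's means in the personal report. The difference in wording between Sections 9 and 12 decides whether a few participants or all of them face the short window.

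**Working it through.** **Stated duration.** Section 11: 2 weeks of baseline + 3 conditions × 2 periods × 2 weeks = 14 weeks. The plan's figure is reproduced, with 0 days between baseline and period 1. Day 1 is a Monday, so day 14 is a Sunday and day 15 a Monday. A day-15 start is inferred from this; no start date is stated.

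**Wear, all ten days visible at review.** Below 80% of 10 means at most 7 days. With four perfect further days, (7 + 4)/14 = 78.6%. Since 0.80 × 14 = 11.2, 12 days are needed, so recovery is impossible.

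**Wear, some days not yet synced.** The scoring is the same, but fewer days are visible at day 10.
- Nine visible: 7 good days plus up to 5 more gives 12/14 = 85.7%, which qualifies.
- There are 1 + 14 + 91 = 106 possible 14-day patterns with at least 12 good days. If unsynced days count as missing, the number showing 7 or fewer good days at review is 0 with ten days visible, 36 with nine and 84 with eight.

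These are counts of patterns, not probabilities. They show that the extension can matter for wear when syncing runs behind the review, as a two-day syncing interval permits.

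**Surveys.** Four a day gives 40 by day 10. With the Sunday survey there are 57 by day 14. The requirement is 0.80 × 57 = 45.6, so 46. At most 17 remain after day 10, so 46 − 17 = 29. Participants with 29, 30 or 31 of 40 fail at day 10 and can still qualify.

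**How many would first qualify on day 14.** This assumes independent survey responses at a constant rate, 57 surveys, and a check each day from day 10. The plan gives no response rate, so a range is shown.

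| Assumed response rate | Enter by catch-up at a single day-14 recheck | First qualify on day 14 with daily checks | Latter, of 60 |
|---|---|---|---|
| 75% | 9.4% | 3.6% | 2.2 |
| 80% | 8.8% | 3.1% | 1.9 |
| 85% | 5.1% | 1.6% | 0.9 |
| 90% | 1.0% | 0.2% | 0.1 |

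The third column fits Section 12, where the assignment is passed on at eligibility. The second fits only a single recheck. If Section 9 is read to mean that nobody is allocated before baseline ends, all 60 could be affected.

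**Effect of lost nights.** The number lost, k, is purely an assumption. Each condition has 2 × 14 = 28 nights, so the adherence ceiling for the first-position condition is 1 − k/28: 96.4%, 89.3% and 82.1% for k = 1, 3 and 5.

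Across the group, let a fraction f be affected, split evenly by sequence. Half of them lose k of 28 placebo nights and half lose k of 56 melatonin nights. The artificial gap is f × (k/56 − k/112) = f × k/112.
- f = 1: 0.9, 2.7 and 4.5 percentage points for k = 1, 3 and 5.
- f = 0.036: at k = 5, 0.036 × 5/112 = 0.16 points.

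**The case for a change.** The best case for a change is that the rule names wear, that Section 12 supports whole-day scoring over the run-in, and that on this scoring a fully synced participant cannot recover. Other scorings, such as pooling wear with surveys (36/50 to 56/70 = 80%) or judging days 11 to 14 alone, give different decisions. The calendar leaves no room for mailing, and the pause option in Section 11 covers participants' own circumstances, not shipping. Pill adherence is a listed secondary feasibility outcome, and a few sentences and one logged date would remove the doubt.

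The arithmetic stands, as do the missing mailing gap and the difference between Sections 9 and 12. The consequences are weaker. A participant who cannot recover on wear is not wrongly admitted or wrongly refused: the same 80% rule withdraws them before randomization. The cost is up to four more days of Fitbit wear and texts, and Section 16 already allows notice from day 10. Making wear recoverable would mean accepting less than 80% of 14 days, which is a trade-off and not a correction.

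Sections 9 and 12 can be read together: the assignment is released during the run-in and the intervention begins after it. The ban on pills during baseline can likewise mean that none is assigned, which is how Section 9 describes the period; read literally, it would bar early mailing. Because the list is prepared in advance and concealed, the day on which an assignment is released does not bias it.

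**Conclusion.** No change follows. With ten complete, synced days and separate whole-day scoring, the extension cannot restore wear (11/14 = 78.6%). It keeps a purpose for surveys and for late-synced days, and the eligibility threshold is the same throughout.

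The delivery window is short for anyone confirmed on day 14: about 0.1 to 2.2 of 60 with daily checks at assumed response rates of 90% down to 75%, and possibly all 60 if allocation waits for the end of baseline. Whether any night is lost is unknown, because the documents give no mailing date, delivery time or period-1 start date. A later start would lose no nights and would only lengthen elapsed time.

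Even in the extreme case of all 60 affected and five nights lost, the result is a 4.5-point gap between placebo and melatonin adherence, a contrast that the plan does not make. Section 12 leaves intervention order out of the analysis, and the System Usability Scale outcome does not depend on these nights. Pill removals are recorded electronically, so the first removal gives a latest possible arrival date for the kit, and an analyst can see where late delivery may explain missing nights. What the catch-up covers, when kits go out and which nights count as assigned are gaps that staff and analysts would fill sensibly.
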